5.3.6 Other Considerations

No other consideration.

5.4 Efficacy Analyses

5.4.1 Primary Efficacy Analyses

The noninferiority analysis of ORR_{24wk} between lenvatinib starting doses of 24 mg and 18 mg will be performed at the 1-sided alpha of 0.025, based on the calculated odds ratio of ORR_{24wk} response (18 mg vs 24 mg) along with its 95% confidence interval (CI) using the Cochran-Mantel-Haenszel (CMH) method, stratified by the randomization stratification factors. The test will be performed per the 95% CI using the noninferiority margin of 0.4. Noninferiority will be declared if the lower limit of the 95% CI for the odds ratio is greater than 0.4.

The point estimate of ORR_{24w} for each group will be summarized with the corresponding 95% CI using asymptotic normal approximation. Treatment difference (18 mg minus 24 mg) will also be estimated with its 95% CI using asymptotic normal approximation.

SENSITIVITY ANALYSIS

A sensitivity analysis will be performed for overall ORR using the same methods as used for ORR_{24wk} .

5.4.2 Secondary Efficacy Analyses

- The following analyses will be performed on PFS, and censoring rules are detailed in [Section 8.4](#):
 - The difference in PFS between lenvatinib starting dose of 24 mg and 18 mg using stratified log-rank test with the randomization stratification factors, tested at an alpha level of 0.05
 - The estimate of the hazard ratio calculated from Cox proportional hazard model on PFS with lenvatinib starting dose as the independent variable and stratified by the randomization stratification factors with a 2-sided 95% CI
 - Kaplan-Meier (KM) estimated quartiles of PFS and their 95% CIs (using the generalized Brookmeyer and Crowley method) per lenvatinib starting dose
 - KM estimated PFS rates at 6, 12, 18 and 24 months and their 95% CIs (using Greenwood log-log formula) per lenvatinib starting dose
 - KM plot of estimated PFS over time

- The analyses of PFS will be repeated for PFS2, and the censoring rule is detailed in [Section 8.4](#)

5.4.3 Other Efficacy Analyses

Duration of response (months), defined as the time from the initial achievement of a response (CR or PR) to the date of first documentation of PD or the date of death, whichever occurs first. It will be summarized for subjects with BOR of CR or PR.

For both endpoints, the censoring rules are the same as those for PFS censoring, when applicable. KM estimated quartiles and their 95% CIs per lenvatinib starting dose, using the generalized Brookmeyer and Crowley method, will be provided.

DCR and CBR will be evaluated using the same method as that used for ORR_{wk24} .

OS will be evaluated using the same method as that used for PFS, and censoring rule is detailed in [Section 8.4](#).

In addition, waterfall plots will be presented by lenvatinib starting dose for the percentage changes from Baseline to postbaseline nadir value in the sum of diameters of target lesions.

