#### 9.7.1.6.3 EXPLORATORY EFFICACY ANALYSES

Duration of response will be defined as the time from the date of first documented response until date of documented progression or death in the absence of disease progression, the end of response should coincide with the date of progression or death from any cause used for the PFS endpoint. The time of the initial response will be defined as the latest of the dates contributing towards the first visit response of PR or CR. If a subject does not progress following a response, then their duration of response will use the PFS censoring time.

Duration of response will be summarized using KM product-limit estimates for each treatment group and presented with 2-sided 95% CIs. The rates of durable SD, DCR (SD, CR, or PR), and CBR (CR, PR, or durable SD) and the corresponding 2-sided 95% CIs will be calculated by treatment group. BOR of SD must be at least 7 weeks following randomization. Durable SD is SD at least 23 weeks after randomization. Treatment differences (percentage-point difference) for 24 mg vs 18 mg will be summarized along with the corresponding 95% CIs based on the normal approximation.

To explore OS, the median survival time and the survival rates at 12, 18, and 24 months will be calculated using KM product-limit estimates for each treatment group and presented with

2-sided 95% CIs. The KM estimates of OS will be plotted over time. Subjects who were enrolled prior to implementation of Amendment 03 and who discontinued lenvatinib treatment due to progressive disease or due to an AE were followed for survival until the date that the last subject transitioned to lenvatinib treatment outside the study (the data cutoff date for this group of 41 subjects). OS data for these subjects will be included in a separate report.

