5.1.1 Primary Endpoints

- ORR_{24wk} as assessed by the investigator using RECIST 1.1. ORR_{24wk} is defined as the proportion of subjects with best overall response (BOR) of complete response (CR) or partial response (PR) at the Week 24 time point or earlier. The BOR for each subject will be determined based on RECIST 1.1 without a requirement for response confirmation.
- Rate of TEAEs with CTCAE grades of 3 or higher within 24 weeks after randomization (as of the Week 24 time point).

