8.4 Censoring Rules

The censoring rules for PFS are explained in [Table 4](#), based upon investigator's tumor assessments and the FDA Guidance for Industry, *Clinical Trial Endpoints for the Approval of Cancer Drugs and Biologics* (2007).

For PFS2, if a subject did not have PD (solely based on the investigator-provided information on the Survival Status eCRF) after starting a new anticancer treatment, or did not die during the study, the subject will be censored on the date last known to be alive.

For OS, in the absence of confirmation of death, subjects will be censored either at the date last known to be alive or the date of data cutoff, whichever is earlier.

Table 4 Censoring Rules for Progression-Free Survival

No.	Situation	Date of Progression or Censoring	Outcome
1	No baseline or postbaseline tumor assessments	Date of randomization	Censored
2	Progression documented between scheduled visits	Date of first radiologic PD assessment	Progressed
3	No progression at the time of data cutoff	Date of last adequate radiologic assessment prior to or on date of data cutoff	Censored
4	New anticancer treatment started	Date of last adequate radiologic assessment prior to or on date of new anticancer treatment	Censored
5	Death before first PD assessment	Date of death	Progressed
6	Death between adequate assessment visits*	Date of death	Progressed
7	Death or progression after more than one missed visit** or after 28 days from the last dose of study treatment	Date of last adequate radiologic assessment before missed tumor assessments	Censored
8	Treatment discontinuation for reasons other than PD	Date of last radiologic assessment before treatment discontinuation	Censored

CR = complete response, PD = progressive disease, PR = partial response, SD = stable disease.

* Adequate tumor assessment is a radiologic assessment of CR, PR, SD, non-CR/non-PD or PD as determined by investigators.

** More than 1 missed visits is defined as having either 1 of the following 2 durations being longer than 18 weeks - 1 day, which is 125 days ($= ((8+1) \times 2 \times 7) - 1$) for subjects on the every-8-week tumor assessment schedule in this study:

- a. Duration between 2 consecutive tumor assessments
- b. Duration between the last adequate tumor assessment and death or PD

The priority of the censoring rules is as follows:

1. If the subject had PD or death, the following sequence will be applied:

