 - If a subject did not have a baseline tumor assessment (No. 1), the subject will be censored on the date of randomization. However, if the subject died within 125 days (18 weeks – 1 day) after randomization and did not receive new anticancer treatment, the date of death will be the PFS event date (not censored).
 - If a subject had new anticancer treatment before PD or death (No. 4), the subject will be censored on the date of the last tumor assessment prior to or on the start date of new anticancer treatment.
 - If PD is reported after the drug discontinuation visit, the subject will be censored at the date of last radiologic assessment before drug discontinuation except when PD occurred at the same visit as drug discontinuation (No. 8). If PD occurred within 4 weeks of drug discontinuation, it will be considered PD at the drug discontinuation visit and counted as a PFS event.
 - If a subject missed more than 1 assessment before PD or death (No. 7), the subject will be censored on the date of the last tumor assessment before PD or death. Note that if a subject is censored by both this criterion and the anticancer treatment criteria, the earliest censoring date will be used.
 - Otherwise, if a subject had an event (No. 2, No. 5 or No. 6), the earliest event date will be used.
2. If a subject did not have PD or death, the censoring date will be the earliest censoring date if the subject met multiple censoring criteria (No. 1, No. 3, No. 4, or No. 7).

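### Duration of response inherits PFS censoring dates that can precede the response itself, for responders first seen to respond after stopping treatment whose PD comes more than 4 weeks after the stop

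*SAP*

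**What the plan says.** - **Start and population (SAP 5.4.3).** The clock starts at the first CR or PR and stops at PD or death. Every responder enters: "It will be summarized for subjects with BOR of CR or PR". The output is Kaplan-Meier quartiles with 95% CIs per starting dose.
- **What counts as a response (SAP 5.1.1).** "The BOR for each subject will be determined based on RECIST 1.1 without a requirement for response confirmation". Neither section restricts responses to scans made before treatment stops, and SAP 5.2.1 analyzes efficacy in all randomized subjects.
- **Censoring of duration of response (SAP 5.4.3).** "For both endpoints, the censoring rules are the same as those for PFS censoring, when applicable". Only one endpoint is described at that point; SAP Section 7 drops duration of clinical benefit.
- **PFS censoring (SAP 8.4).** For a stop not due to PD, row 8 of Table 4 uses: "Date of last radiologic assessment before treatment discontinuation". PD found when treatment stops, or up to 4 weeks later, remains an event. For PD after that, the priority list says: "If PD is reported after the drug discontinuation visit, the subject will be censored at the date of last radiologic assessment before drug discontinuation". The new-therapy rule stands earlier in that list. For subjects with neither PD nor death, the list names rows 1, 3, 4 and 7, but not row 8.
- **Protocol 9.7.1.6.3.** "If a subject does not progress following a response, then their duration of response will use the PFS censoring time". For responders who do progress, the end of response is tied to the PD or death date used for PFS.
- **Scans after the stop.** Protocol 9.3.3, 9.5.1.2.4 and Table 7 footnote r keep 8-weekly scans going after a stop without PD. Footnote r also requires an Off-treatment scan if more than 4 weeks have passed since the last one.

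**The concern.** PFS starts at randomization, so moving its end back to an earlier on-study scan shortens the time but leaves it valid. Duration of response starts later, at the first CR or PR. If that response is first seen after treatment has stopped, moving the end back to the last scan before the stop goes past the start. No rule in SAP 5.4.3 or 8.4 keeps the end of response on or after the response date.

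Such a subject counts as a responder but contributes no response time and no PD to the estimate of how long responses last. The trial hopes that 18 mg is better tolerated, so early stops for toxicity, and with them the subjects lost this way, could be unequal between arms. Two programmers could also repair the impossible value differently, because the SAP gives no rule for it.

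**Working it through.** **1. The plan's own figure.** The only computed number in the reused rules is the missed-visit threshold: ((8+1)×2×7)−1 = 125 days. It reproduces and is not in dispute.

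**2. The rules applied to constructed timelines.** Randomization and first dose are on day 0. Duration = end day − response day + 1, and 1 month = 30.4375 days (SAP 8.3). No new anticancer therapy is given.

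| Case | Timeline | Rule applied | End day | Duration |
|---|---|---|---|---|
| 1 | SD 56, stop 90, first PR 112, PD 224 | Row 8 and priority list | 56 (censored) | 56−112+1 = −55 days (−1.8 months) |
| 1 | same | PD counted | 224 (event) | 224−112+1 = 113 days (3.7 months) |
| 2 | as case 1, no PD, last scan 280 | Table 4 row 8 | 56 (censored) | −55 days |
| 2 | same | Priority item 2, via row 3 | 280 (censored) | 280−112+1 = 169 days |
| 3 | No stop: SD 56, two missed scans, first PR 224, PD 280 | Row 7 (gap 224−56 = 168 > 125) | 56 (censored) | 56−224+1 = −167 days |
| 3 | same | Priority text, last scan before PD | 224 (censored) | 1 day |
| 4 | PR 56, stop 90, PD 224 | Row 8 and priority list | 56 (censored) | 1 day |

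Case 1 is the core: the end date follows from the stated rules and precedes the response. In case 2 the two parts of SAP 8.4 disagree, and only one gives an impossible value. Case 3 is a second route, through missed scans, with a similar disagreement. In case 4 the value is valid but almost empty.

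**3. Effect on the Kaplan-Meier estimate.** A subject censored before the first event time is in no risk set. In a check with times 3, 5, 8, 8, 12, 15 and 20 months (events at 3, 8, 8 and 15), adding two subjects censored at −1.8 and −2.1 months left every risk set and estimate at the event times unchanged. So did recoding both to 1 day. No false value enters, but the observed response time and PD are lost.

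**4. Size.** Responders per arm: 76 × 0.544 = 41.3, using the planning rate in SAP Section 4. The documents do not say how many first responses follow a stop. Assumptions: first responses at days 53, 109 and 165 in proportions 0.55, 0.30 and 0.15; a constant rate of stopping for AEs with a fraction p stopped by day 168; and a response still just as likely to be seen up to W days after the stop. With λ = −ln(1−p)/168,

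share = Σ wₖ [exp(−λ·max(tₖ−W, 0)) − exp(−λtₖ)].

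| p | W = 30 days | W = 56 days |
|---|---|---|
| 5% | 0.9% | 1.6% |
| 10% | 1.8% | 3.3% |
| 15% | 2.7% | 5.0% |

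Per arm this runs from 41.3 × 0.009 = 0.4 to 41.3 × 0.050 = 2.1 responders, before removing those with PD within 4 weeks of the stop, those given new therapy before PD, and those without PD by the data cutoff.

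**The case against.** **The inheritance is qualified, and derivations sit elsewhere.** The sentence in SAP 5.4.3 applies the PFS rules only where they fit, and SAP Section 9 leaves derivations to a separate dataset specification. A careful programmer would notice a negative time. That is fair, but the qualifier does not say which rows are switched off or what date replaces them, and the protocol sentence carries no such qualifier. The protocol does not settle case 1 either. The sentence quoted above concerns responders who do not progress. For those who do, it points to the PD date used for PFS, and there is none because PFS is censored.

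**Several rules remove cases.** A reader might infer that every late first responder with a later PD gets a negative duration. The documents do not support that. PD within 4 weeks of the stop is an event. New anticancer therapy before PD is handled first, and it censors at a scan on or after the response if the response scan preceded that therapy. For subjects without PD or death, priority item 2 gives a positive time.

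**A date before randomization.** If only the baseline scan precedes the stop, a reader might infer that the response ends before randomization. With a baseline scan on day −7 and PR on day 56 this would be −7−56+1 = −62 days, or −55 if the end were floored at randomization. The documents leave this open: the Table 4 footnote defines an adequate assessment by response categories that a baseline scan does not have, and row 1 uses the randomization date. It would also be a fault in PFS itself. The point does not depend on it.

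**Dropped subjects and a biased comparison.** A reader might infer that the SAP deletes negative durations, or that the arms are formally compared on selected responders. No text says that negative times are dropped; their lack of influence is a property of the estimator. Only per-dose quartiles are planned, with no test on this endpoint.

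**Conclusion.** The point holds in a narrow form. A responder whose first CR or PR is on a scan after a stop not due to PD, and whose PD is reported more than 4 weeks after that stop with no new anticancer therapy in between, is given a censoring date earlier than the response. The duration is negative, and the observed response and PD add nothing to the Kaplan-Meier estimate. For the same kind of responder without PD or death, Table 4 row 8 and priority item 2 contradict each other.

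The size is small: at most about 0 to 2 of roughly 41 responders per arm. This rests on assumed stopping rates of 5% to 15% by Week 24, an assumed timing of first response, and response being as likely shortly after the stop as on treatment. The endpoint is exploratory and untested, and the primary analysis of ORR24wk is unaffected. It is still worth correcting, because a stated rule that yields an impossible value is wrong as written and cheap to repair.

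**What to change.** In SAP 5.4.3, replace the censoring sentence, including its reference to two endpoints, by:

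*PFS censoring rules apply to duration of response only when the resulting date is on or after the date of first response. Otherwise, duration of response ends at first documented PD or death occurring before any new anticancer therapy, or is censored at the last adequate assessment on or after first response and on or before the start of new anticancer therapy. In both situations, missed-visit gaps are counted only from first response.*

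Then:

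- Reconcile Table 4 row 8 with priority item 2, stating whether a subject who stops for a reason other than PD, and has neither PD nor death, is censored at the stop or at the last scan. This decision also governs PFS.
- Record in SAP Section 7 that, for these subjects, the end of response may differ from the date used for PFS, which departs from protocol 9.7.1.6.3.

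Under the new text, case 1 becomes 113 days with an event. Case 2 becomes 169 days, censored, under either list. Case 3 becomes 280−224+1 = 57 days with an event. Case 4 stays at 1 day: the change is deliberately confined to impossible dates and does not lift row 8 for all responders who stop before PD.

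The cost is a separate derivation for a few subjects, whose end dates then differ from PFS and rely on post-treatment scans. No new data are needed.

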5.3.3 Multiple Comparisons/Multiplicity

Not applicable.

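### SAP 5.4.3 carries the ORR24wk noninferiority rule (odds ratio margin 0.4) to DCR and CBR, where the margin has no basis, and adds an OS test, both beyond the protocol and undeclared in SAP 7

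*SAP*

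**What the plan says.** **DCR and CBR.** SAP 5.4.3 says "DCR and CBR will be evaluated using the same method as that used for" ORR24wk. SAP 5.4.1 defines that method. The noninferiority analysis "will be performed at the 1-sided alpha of 0.025", using a stratified Cochran-Mantel-Haenszel odds ratio, and "Noninferiority will be declared if the lower limit of the 95% CI for the odds ratio is greater than 0.4". Each arm's rate "will be summarized with the corresponding 95% CI using asymptotic normal approximation", and so is the difference. SAP 5.4.3 excludes no part of this.

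Protocol 9.7.1.6.3 plans less: rates with 95% CIs by arm, and differences that "will be summarized along with the corresponding 95% CIs based on the normal" approximation. It has no odds ratio, margin or test for these endpoints.

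**Time-to-event endpoints.** SAP 5.4.2 compares PFS "using stratified log-rank test with the randomization stratification factors, tested at an alpha level of 0.05" and repeats the analysis for PFS2. SAP 5.4.3 adds "OS will be evaluated using the same method as that used for PFS". Protocol 9.7.1.6.2 already plans the stratified log-rank test and Cox hazard ratio for PFS and PFS2, without an alpha level. For OS, Protocol 9.7.1.6.3 plans only Kaplan-Meier medians, rates at 12, 18 and 24 months, and a plot.

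**Multiplicity and declared changes.** SAP 5.3.3, "Multiple Comparisons/Multiplicity", is marked as not applicable. SAP 7 records the biomarker analysis set, the dropping of duration of clinical benefit and new ECG categories. It mentions neither DCR/CBR nor OS.

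**The concern.** A noninferiority margin belongs to the endpoint for which it was derived. The 0.4 comes from the effect of lenvatinib on 24-week response against placebo. Applied by cross-reference to disease control and clinical benefit, it becomes a decision rule that nobody has justified for those endpoints. Because it works on the odds ratio scale, its power falls as the rate approaches 1. DCR and CBR count all responders plus stable disease, so they lie at or above the response rate. Two equally effective doses could then be reported as not shown noninferior on disease control.

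The same cross-reference brings in normal-approximation limits for a single rate, which behave poorly close to 1. For OS, a protocol description becomes a test at a stated alpha. With no statement of which tests are formal, a reader of the study report cannot tell a confirmatory result from an incidental one. In a trial that asks whether two doses are comparable, a non-significant difference could be taken as support for that.

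**Working it through.** **Inputs from the documents.** 76 per arm, 1:1; margin 0.4; 1-sided alpha 0.025; 24 mg ORR24wk 54.4% (142/261) against 0.8% on placebo (1/131); lower 95% limit of that odds ratio 21.4; 70% retention (SAP 4, Protocol 9.7.2).

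**1. The plan's own figures.**
- Odds ratio = (142 × 130)/(119 × 1) = 155.1. Its lower limit is exp[ln 155.1 − 1.96 × √(1/142 + 1/119 + 1/1 + 1/130)] = 21.4, as stated.
- Margin = 21.4^(−0.3) = 0.399, stated as 0.40.
- n per arm = 2(1.960 + 0.842)² / [0.544 × 0.456 × (ln 0.4)²] = 75.4, so 76. Power at 76 is 80.3%.

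The sizing for ORR24wk reproduces.

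**2. Does the margin transfer?** Under the same 70% retention rule, 0.4 requires a lower odds ratio limit against placebo of 0.4^(−1/0.3), about 21. The documents give no placebo DCR or CBR, so nothing shows that limit for either endpoint.

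**3. Behaviour of the borrowed rule.** No DCR or CBR rate is given. The overall response rate in Study 303 was 64.8% (Protocol 7.1), and both endpoints include every responder, so rates from 70% upward are assumed.

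Rate allowed at the margin: 0.4 × odds / (1 + 0.4 × odds). At 90%, odds are 9, so 3.6/4.6 = 78.3%.

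Power with identical arms is approximately Φ(|ln 0.4| × √(76p(1 − p)/2) − 1.96). The table gives the binomial enumeration of the unstratified odds-ratio interval. It also gives the exact coverage of the normal-approximation 95% interval for one rate (n = 76) and how often its upper limit exceeds 100%.

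| True rate | Allowed at 0.4 | Rule met, identical arms | Coverage, single rate | Upper limit >100% |
|---|---|---|---|---|
| 54.4% | 32.3% | 81% | 95% | 0% |
| 70% | 48.3% | 72% | 95% | 0% |
| 80% | 61.5% | 61% | 94% | 0% |
| 85% | 69.4% | 52% | 93% | 0.2% |
| 90% | 78.3% | 38% | 95% | 5% |
| 95% | 88.4% | 19% | 89% | 45% |
| 97% | 92.8% | 8-9% | 90% | 71% |

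At 95% the third column is 19% if tables with an empty cell count as failures and 20% if 0.5 is added to them. Coverage oscillates with the rate (for example 94.1% at 92%, 90.2% at 93%), so isolated dips near 90% also occur between the tabulated values. Wilson coverage at 95% is 94%. The rule's type I error at the margin is 1.8% to 2.6% across these rates, so it is not too liberal.

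**4. Unadjusted tests.** The sidedness of the 0.05 level is not stated; 2-sided is assumed. For PFS, PFS2 and OS the chance of at least one false positive is at most 3 × 0.05 = 15%, and 1 − 0.95³ = 14.3% if independent. Simulation gives 13.5%, 12.5%, 10.9% and 8.4% at assumed common correlations of 0.3, 0.5, 0.7 and 0.9.

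**The case against.** The strongest reply is that the SAP attaches a declaration rule to ORR24wk alone. DCR, CBR and OS are exploratory, and the cross-reference may have meant only the odds ratio, rates, difference and intervals. That reading is possible. But SAP 5.4.3 excludes nothing, and SAP 5.4.1 uses almost the same phrase for overall ORR as a sensitivity analysis of the noninferiority result. A programmer could reasonably produce the test, so the ambiguity needs closing.

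On intervals, the protocol itself specifies the normal approximation for the DCR and CBR differences. Coverage of the difference interval is 94.6% to 95.7% for rates of 70% to 97%. That stands: the difference intervals need no change, and only the single-rate limits at extreme rates do.

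A reader might infer three stronger things that the documents do not support.
- *That error control in the trial fails at 14%.* The primary 1-sided 0.025 is untouched. The protocol already plans the PFS and PFS2 log-rank tests, and no success claim is attached to PFS, PFS2 or OS. These endpoints share deaths, so independence is doubtful, and 14.3% is close to the 15% ceiling.
- *That low power for PFS is a design fault.* The trial was sized on ORR24wk only. Any PFS power figure rests on a hazard ratio and accrual pattern that the documents do not give.
- *That the borrowed rule yields unfounded positive claims, or usually fails.* Its type I error is near nominal, so the risk is too few positive results. It is still met in 52% of trials at a rate of 85%, and fails more often than not only above roughly 86%.

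**Conclusion.** The point holds in a limited form. As written, SAP 5.4.3 applies to DCR and CBR a noninferiority rule whose margin has no basis for them. For DCR/CBR (odds ratio and rule) and OS (log-rank test at 0.05 and hazard ratio), the SAP exceeds the protocol's estimation plan without an entry in SAP 7.

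The practical size depends on rates that the documents do not give. With identical doses the rule would be met 61% of the time at 80%, falling to 19% at 95%. Single-rate limits are broadly adequate up to about 90% and weak at 95% and above. These figures assume 76 per arm and an unstratified odds ratio in place of the stratified one.

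The primary conclusion is not at risk. The 15% ceiling for the three time-to-event tests matters only if their p-values are read as confirmatory. The SAP does not say that they will be, but it does not rule it out. This should be corrected before database lock.

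**What to change.** - **SAP 5.4.3, DCR and CBR:** report the rate in each arm with Wilson or exact 95% limits, and the difference with its 95% CI. State that no noninferiority conclusion is drawn.
- **SAP 5.4.3, OS:** return to the protocol's Kaplan-Meier description, or keep the test and hazard ratio and declare the change in SAP 7. Any other departure from Protocol 9.7.1.6.3 that is kept should also be listed there.
- **SAP 5.4.2:** keep the protocol-planned log-rank tests and hazard ratios for PFS and PFS2, and label the p-values nominal.
- **SAP 5.3.3:** replace the present entry with a statement that ORR24wk noninferiority is the only formal efficacy test, that other p-values are unadjusted, and that p > 0.05 on another endpoint is not evidence of comparability.

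The cost is SAP wording only, with no effect on sample size, data collection or the primary analysis. The sponsor gives up formal significance or noninferiority statements on secondary and exploratory endpoints.
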